5.5 Premedication Plan

Prior to ALN-TTR02, patients will receive the following premedications:

- Intravenous dexamethasone (10 mg) or equivalent, administered at least 60 minutes prior to the start of the infusion of ALN-TTR02;
- Oral paracetamol (500 mg) or equivalent at least 60 minutes prior to the start of the infusion of ALN-TTR02;
- Intravenous H2 blocker (e.g., ranitidine 50 mg, famotidine 20 mg, or equivalent other H2 blocker dose) at least 60 minutes prior to the start of the infusion of ALN-TTR02; and
- Intravenous H1 blocker: diphenhydramine 50 mg (or equivalent other IV H1 blocker available at the study site) at least 60 minutes prior to the start of the infusion of ALN-TTR02. Hydroxyzine or fexofenadine 25 mg PO or cetirizine 10 mg PO may be substituted for any patient who does not tolerate IV diphenhydramine or other IV H1 blocker.

Patients will be started on the above premedication regimen. However, modifications may be made to the premedication regimen after consultation with the medical monitor either due to a patient's inability to tolerate one or more of the premedications or to the occurrence of IRRs unresponsive to slowing of the infusion rate.

- If a patient is having difficulty tolerating the steroid premedication regimen (e.g., patient develops uncontrolled hyperglycemia, altered mental status, or other complication), then lowering of the steroid premedication may be allowed for that patient after consultation with the medical monitor.
- If after consultation with the medical monitor, it is agreed that an individual patient's steroid premedication will be lowered, then the following steps **must be followed**:
 - 1) If the current steroid dosage is 10 mg intravenous dexamethasone or equivalent, then the patient may be lowered in increments no greater than 2.5 mg intravenous dexamethasone or equivalent.
 - 2) After each incremental lowering below 10 mg intravenous dexamethasone or equivalent, the patient must receive three consecutive intravenous doses of patisiran without IRR and continued signs or symptoms of steroid intolerance before further reductions in steroid premedications.
 - 3) The premedication steroid dosage should not be reduced below 5 mg intravenous dexamethasone or equivalent.

Alternatively, if a patient experiences an IRR when 10 mg or less of intravenous dexamethasone or equivalent is used as the steroid premedication, then proceed to Section 5.11.

Further details can be found in the Study Reference Manual.

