k Two assessments will be performed on separate days at Screening/Baseline and then approximately every 6 months. The Screening/Baseline assessments must be performed within 14 days prior to the first dose of study drug (Day 0). The second (repeat) assessment must be conducted at least 24 hours after the first assessment. In addition, every effort should be made to conduct the 2 assessments no greater than 7 days apart.

l Hand grip strength will be measured using a dynamometer held in the dominant hand. Every effort will be made to use the same device for a patient throughout the duration of the study.

- m Patient will walk without assistance for 10 meters.
- n Two 3-mm skin punch biopsies are to be obtained. One will be obtained from the distal lower leg, when a patient's clinical status allows, and one from the distal thigh.
- o Quality of life and disability assessments will include the EQ5D and R-ODS questionnaires.
- p The following premedications will be administered at least 60 minutes prior to the start of the infusion of ALN-TTR02: dexamethasone (10 mg IV, or equivalent), paracetamol (PO 500 mg, or equivalent), IV H2 blocker (e.g., ranitidine 50 mg, famotidine 20 mg, or equivalent other H2 blocker dose), and IV H1 blocker (e.g., diphenhydramine 50 mg or equivalent; hydroxyzine or fexofenadine 25 mg PO or cetirizine 10 mg PO may be substituted for any patient who does not tolerate IV diphenhydramine or other IV H1 blockers). Based on results from the ALN-TTR02-002 study, the following alternative premedication regimen can be used: dexamethasone (8 mg, or equivalent), paracetamol (500 mg, or equivalent), H2 blocker (e.g., 150 mg ranitidine, or 20 mg famotidine, or equivalent other H2 blocker dose), and H1 blocker (10 mg cetirizine, 25 mg hydroxyzine, fexofenadine or equivalent may be substituted) self-administered per os (PO) the evening before study drug administration. At least 60 minutes prior to the start of study drug infusion, dexamethasone (20 mg PO, or equivalent), paracetamol (500 mg PO, or equivalent), an H2 blocker (PO), and an H1 blocker (PO) will be administered by study site personnel.
- q The infusion site will be assessed for any localized reaction pre-dose, during infusion, at the end of the infusion, for 30 minutes after the infusion.
- r Plasma PK samples will be collected pre-dose (within 1 hour of planned dosing start), EOI, and 2 hrs post-dose (± 5 min), except on Days 0 and 224 for subjects in the PK/PD Subgroup.

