- l The following premedications will be administered at least 60 minutes prior to the start of the infusion of ALN-TTR02: dexamethasone (10 mg IV, or equivalent), paracetamol (PO 500 mg, or equivalent), IV H2 blocker (e.g., ranitidine 50 mg, famotidine 20 mg, or equivalent other H2 blocker dose), and IV H1 blocker (e.g., diphenhydramine 50 mg or equivalent; hydroxyzine or fexofenadine 25 mg PO or cetirizine 10 mg PO may be substituted for any patient who does not tolerate IV diphenhydramine or other IV H1 blockers). Based on results from the ALN-TTR02-002 study, the following alternative premedication regimen can be used: dexamethasone (8 mg, or equivalent), paracetamol (500 mg, or equivalent), H2 blocker (e.g., 150 mg ranitidine, or 20 mg famotidine, or equivalent other H2 blocker dose), and H1 blocker (10 mg cetirizine, 25 mg hydroxyzine, fexofenadine or equivalent may be substituted) self-administered per os (PO) the evening before study drug administration. At least 60 minutes prior to the start of study drug infusion, dexamethasone (20 mg PO, or equivalent), paracetamol (500 mg PO, or equivalent), an H2 blocker (PO), and an H1 blocker (PO) will be administered by study site personnel.
- m The infusion site will be assessed for any localized reaction pre-dose, during infusion, at the end of the infusion, for 30 minutes after the infusion.
- n Plasma PK samples will be collected pre-dose (within 1 hour of planned dosing start), EOI and 2 hours post dose.
- o For each dose, urine PK samples will be collected pre-dose and 2 hours after dosing with ALN-TTR02.

- p For patients in the PK/PD subgroup, blood samples for TTR, RBP, and vitamin A will be collected on Day 756: prior to administration of premedications and a blood sample will also be collected 24 hours, 3, 7 and 17 days after dosing with ALN-TTR02.
- q On Day 756, patients in the PK/PD sub-group will have PK samples taken at predose, end of infusion, 1, 2, 4, 6, and 24 hours post-infusion. In addition, a plasma PK sample will also be collected 3, 7, and 17 days (± 1 day) after dosing with ALN-TTR02 for the study visits noted. The windows for sampling are ± 5 minutes for the 1, 2, 4, and 6 hour sampling periods; and ± 120 minutes for the 24 hour sampling period.

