4.6.6. Premedication

All patients received premedication in order to reduce the potential of an IRR. The original premedication regimen as outlined below was used at the start of the study. A subset of patients experienced AEs suspected to be related to steroids (eg, flushing) and were transitioned to a modified premedication regimen, with a reduced dose of corticosteroid to mitigate these events, as sanctioned in the protocol. After observing that the subset of patients tolerated the lower corticosteroid dose with no increase in IRRs, the protocol was amended (Global Amendment 1) to transition the rest of the patients to the modified premedication regimen (see below).

The following original premedication regimen was used prior to Global Amendment 1:

- Dexamethasone 8 mg PO or equivalent administered the evening before dosing and 20 mg PO at least 60 minutes prior to the start of the infusion of patisiran;
- Paracetamol 500 mg PO or equivalent administered the evening before dosing and at least 60 minutes prior to the start of the infusion of patisiran;
- H2 blocker PO (e.g., ranitidine 150 mg or famotidine 20 mg or equivalent other H2 blocker dose) administered the evening before dosing and at least 60 minutes prior to start of the infusion of patisiran; and
- H1 blocker PO, 10 mg cetirizine or equivalent (hydroxyzine 25 mg or fexofenadine could be substituted if patient did not tolerate cetirizine) administered the evening before dosing and at least 60 minutes prior to start of the infusion of patisiran.

The following modified premedication regimen was instituted with Global Amendment 1:

- Dexamethasone 10 mg IV or equivalent, administered at least 60 minutes prior to the start of the infusion of patisiran;
- Paracetamol 500 mg PO or equivalent at least 60 minutes prior to the start of the infusion of patisiran;
- H2 blocker IV (e.g., ranitidine 50 mg, famotidine 20 mg, or equivalent other H2 blocker dose) at least 60 minutes prior to the start of the infusion of patisiran; and
- H1 blocker IV, diphenhydramine 50 mg (or equivalent other IV H1 blocker available at the study site) at least 60 minutes prior to the start of the infusion of patisiran. Hydroxyzine

25 mg PO or fexofenadine 30 or 60 mg PO or cetirizine 10 mg PO could be substituted for any patient who did not tolerate IV diphenhydramine or other IV H1 blocker.

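### Appendix 2 still permits, with no stated trigger or medical-monitor consultation, the 8 mg plus 20 mg oral dexamethasone premedication that the SAP says was replaced, in conflict with Protocol Sections 5.5 and 5.11

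*Protocol*

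**What the plan says.** **Protocol Section 5.5** lists one premedication regimen. Its steroid element is "Intravenous dexamethasone (10 mg) or equivalent, administered at least 60 minutes prior to the start of the infusion of ALN-TTR02". It continues: "Patients will be started on the above premedication regimen. However, modifications may be made to the premedication regimen after consultation with the medical monitor". The grounds it gives for a change are intolerance of a premedication, or IRRs that slowing the infusion does not resolve. The synopsis and the footnotes to Tables 1-1 and 1-2 (every-3-week schedule) give the same regimen and no alternative steroid regimen.

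**Protocol Section 5.11** covers increases in steroid premedication. They follow an IRR and agreement with the medical monitor, and are capped at 20 mg IV on the day plus 8 mg by mouth the night before.

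**Protocol Appendix 2** (every-4-week schedule) opens footnote p of Table 12-1 and footnote l of Table 12-2 with the Section 5.5 steroid dose: "dexamethasone (10 mg IV, or equivalent), paracetamol (PO 500 mg, or equivalent"). Both footnotes then add: "Based on results from the ALN-TTR02-002 study, the following alternative premedication regimen can be used: dexamethasone (8 mg, or equivalent"), taken by mouth the evening before. For the day itself they say: "At least 60 minutes prior to the start of study drug infusion, dexamethasone (20 mg PO, or equivalent), paracetamol (500 mg PO, or equivalent"). No condition is attached to the choice.

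**SAP Section 4.6.6** gives 8 mg by mouth the evening before plus 20 mg by mouth on the day as the original regimen, in use before Global Amendment 1. It reports that a subset of patients with suspected steroid-related adverse events moved to a lower dose, and that "the protocol was amended (Global Amendment 1) to transition the rest of the patients to the modified premedication regimen".

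**The concern.** Two footnotes in the current protocol leave open, as a free choice, a regimen that the SAP describes as superseded for a tolerability reason. This is operative text in a schedule of assessments, not an entry in a log of changes. A site reading Section 5.5 would start at 10 mg IV and call the medical monitor before changing anything. A site reading the Appendix 2 footnote could give the oral regimen from the first infusion without a call.

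The primary objective is long-term safety, and Section 1.6.2.3 itself names glucocorticoid premedication as a possible contributor to bone loss in these patients. The conditions under which a patient can receive the larger steroid dose should therefore not depend on which part of the protocol the site consults.

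**Working it through.** The documents state neither a 28 mg total nor a ratio, so there is no plan figure to reproduce. The check sets the passages side by side and then does the arithmetic.

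**Conditions attached to each steroid regimen**

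| Place | Steroid per infusion (nominal dexamethasone) | Stated condition |
|---|---|---|
| Section 5.5 | 10 mg IV | Starting regimen; change after medical-monitor consultation |
| Section 5.11 | Up to 20 mg IV + 8 mg oral | After an IRR, with medical-monitor agreement |
| Tables 1-1 and 1-2 footnotes | 10 mg IV | No alternative offered |
| Tables 12-1 and 12-2 footnotes, first regimen | 10 mg IV | None |
| Tables 12-1 and 12-2 footnotes, alternative | 8 mg oral + 20 mg oral | None |

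The last row conflicts with the first two. It reaches the nominal Section 5.11 maximum (20 + 8 = 28 mg) without the IRR or the consultation that Section 5.11 requires, and it bypasses the starting rule of Section 5.5.

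**Size per infusion**

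- Alternative: 8 + 20 = 28 mg.
- Section 5.5: 10 mg.
- Ratio: 28 / 10 = 2.8. For the day-of-infusion dose alone: 20 / 10 = 2.0.

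**Size across the two schedules**

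- Every 4 weeks, Day 0 to Day 756: 756 / 28 + 1 = 28 infusions.
- Every 3 weeks, Day 0 to Day 735: 735 / 21 + 1 = 36 infusions.
- Every-4-week alternative: 28 × 28 = 784 mg over the study.
- Every-3-week standard: 36 × 10 = 360 mg. Ratio: 784 / 360 = 2.18.
- Every-4-week first-listed regimen: 28 × 10 = 280 mg. Ratio to the every-3-week standard: 280 / 360 = 0.78.

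So 2.8 is the ratio between two options at one infusion. It is not the gap between the two sets of tables.

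**Who could meet the footnotes**

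- Protocol Section 5.6 keeps both the 3-week and the 4-week interval, and Section 5.7 lets the interval be lengthened for a patient after a drug-related adverse event.
- The opening paragraph of Appendix 2 says that the every-3-week schedule is in Table 12-1, but Table 12-1 is the every-4-week table. A reader on the 3-week schedule can be sent to the footnote by mistake.
- On the other side, SAP Section 1.2.1 describes every-3-week dosing only, the PK summary days in SAP Section 4.5.2 (22, 43, 64, 85 and so on) begin at 21-day spacing, and the exposure formula in SAP Section 4.6.1 adds 21 days.

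**The case against.** The best reply is that the oral regimen is only an option. Both sets of tables put 10 mg IV first, so a site that follows the lead regimen gives the same dose per infusion everywhere. The alternative also does not exceed the nominal ceiling in Section 5.11. And the documents show no patient treated every 4 weeks; the SAP is built around every-3-week dosing. All of this stands. It limits the size and reach of the problem, but two current footnotes still remove conditions that Sections 5.5 and 5.11 impose.

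Three stronger readings are tempting and should not be drawn.

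- A reader might infer that steroid exposure differs 2.8-fold according to the table a site uses. It does not: the difference arises only if the alternative is chosen. Over the study, the every-4-week alternative against the every-3-week standard is about 2.2-fold, and without the alternative the ratio is 0.78.
- A reader might infer that every place listing the 10 mg regimen also requires consultation before a change. Among the passages that list it as the regimen to be given, only Section 5.5 carries that rule; the synopsis and the Table 1-1 and 1-2 footnotes do not.
- A reader might infer that the SAP comparison of original and modified regimens is compromised because it assigns patients by amendment date. SAP Section 4.6.6 states no such rule. It says that a subset switched before the amendment, counts a patient who switches in both categories, and lists the day of change and the exposure under each regimen. Its wording names only the switch from original to modified, but a return to the original would show in the premedication listings.

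**Conclusion.** The conflict holds as an internal contradiction in the current protocol. Appendix 2 permits, unconditionally, the oral dexamethasone regimen that the SAP describes as replaced, while Section 5.5 sets a different starting regimen with a consultation rule and Section 5.11 makes the same nominal 28 mg conditional on an IRR and consultation.

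Its size is at most 2.8-fold in dexamethasone per infusion (28 versus 10 mg), and only where the alternative is given. That figure counts nominal milligrams. One regimen is oral and the other intravenous, and the documents give no conversion, so it is not a ratio of systemic exposure.

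It matters only for patients managed under Appendix 2, or sent there by the wrong cross-reference. The documents give no count of such patients, and the number may be zero. The point is worth correcting because it concerns patient safety and costs little, not because it threatens an analysis.

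**What to change.** The sponsor should reconcile footnote p of Table 12-1 and footnote l of Table 12-2 with Sections 5.5 and 5.11, so that these passages no longer contradict one another on when the oral regimen may be given. Which regimen applies, and on what condition, is for the sponsor to decide.

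The opening paragraph of Appendix 2 should also be corrected so that it no longer gives Table 12-1 as the every-3-week schedule; that schedule is in Tables 1-1 and 1-2.

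The cost is two footnotes and one cross-reference in the protocol. No SAP change is needed.

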Appendix 3: New York Heart Association Classification of Heart Failure

Class	Symptomatology
I	No symptoms. Ordinary physical activity such as walking and climbing stairs does not cause fatigue or dyspnea.
II	Symptoms with ordinary physical activity. Walking or climbing stairs rapidly, walking uphill, walking or stair climbing after meals, in cold weather, in wind or when under emotional stress causes undue fatigue or dyspnea.
III	Symptoms with less than ordinary physical activity. Walking one to two blocks on the level and climbing more than one flight of stairs in normal conditions causes undue fatigue or dyspnea.
IV	Symptoms at rest. Inability to carry on any physical activity without fatigue or dyspnea.

Protocol ALN-TTR02-003**Amendment 1.2 Summary of Changes****A Phase 2, Multicenter, Open-Label, Extension Study to Evaluate the Long-Term Safety, Clinical Activity, and Pharmacokinetics of ALN-TTR02 in Patients With Familial Amyloidotic Polyneuropathy Who Have Previously Received ALN-TTR02**

Changes included in Amendment 1.2 to Protocol ALN-TTR02-003, dated 26 November 2013, are detailed below.

Text added is indicated by **bold** font.

Section	Prior Text	New Text
Protocol Synopsis – Inclusion Criteria	
4. Adequate liver function, demonstrated by an aspartate transaminase (AST) and alanine transaminase (ALT) level $\leq 2.5 \times$ the upper limit of normal (ULN), total bilirubin within normal limits, albumin >3 g/dL, and international normalized ratio (INR) ≤ 1.2.
	
4. Adequate liver function, demonstrated by an aspartate transaminase (AST) and alanine transaminase (ALT) level $\leq 2.5 \times$ the upper limit of normal (ULN), total bilirubin within normal limits, albumin >3 g/dL, and international normalized ratio (INR) ≤ 1.2 (patients on warfarin with an INR of ≤ 3 will be allowed).

4.2 Inclusion Criteria	
4. Adequate liver function, demonstrated by an aspartate transaminase (AST) and alanine transaminase (ALT) level $\leq 2.5 \times$ the upper limit of normal (ULN), total bilirubin within normal limits, albumin >3 g/dL, and international normalized ratio (INR) ≤ 1.2.
	
4. Adequate liver function, demonstrated by an aspartate transaminase (AST) and alanine transaminase (ALT) level $\leq 2.5 \times$ the upper limit of normal (ULN), total bilirubin within normal limits, albumin >3 g/dL, and international normalized ratio (INR) ≤ 1.2 (patients on warfarin with an INR of ≤ 3 will be allowed).

7.1.4.	Algorithms for Setting Normal Deviates and Points	43
7.2.	Euro Quality of Life-5-Dimension 5-Level (EQ-5D-5L)	48
7.3.	Rasch-Built Overall Disability Scale (R-ODS)	49
7.4.	Composite Autonomic Symptom Score (COMPASS-31).....	50

TABLES INCLUDED IN THE TEXT

	Page
Table 1-1: Schedule of Assessments for Year 1 — ALN-TTR02 Administered Once Every 3 Weeks	12
Table 1-2: Schedule of Assessments for Year 2 — ALN-TTR02 Administered Once Every 3 Weeks	17
Table 2-1: All Percentiles Table	45
Table 2-1: Extended Percentiles Table	47

LIST OF ABBREVIATIONS AND DEFINITION OF TERMS

Abbreviation	Definition
ADA	Anti-drug antibodies
AE	Adverse event
ATC	Anatomic therapeutic class
ATTR	Transthyretin-mediated amyloidosis
AUC	Area under the plasma concentration-time curve
COMPASS 31	Composite Autonomic Symptom Score
CRO	Contract Research Organization
CSR	Clinical study report
CTCAE	Common Terminology Criteria for Adverse Events
ECG	Electrocardiogram
eCRF	Electronic case report form
eGFR	Estimated glomerular filtration rate
ELISA	Enzyme linked immunosorbent assay
EOI	End of infusion
ET	Early termination
EU	European Union
FAC	Familial amyloidotic cardiomyopathy
FAP	Familial amyloidotic polyneuropathy
H1/H2 blocker	Histamine H1/H2 receptor antagonist
HRdb	Heart rate response to deep breathing
ICH	International Conference on Harmonisation
IENFD	Intraepidermal nerve fiber density
IRR	Infusion-related reaction
IV	Intravenous(ly)
LNP	Lipid nanoparticles
mBMI	Modified body mass index
MedDRA®	Medical Dictionary for Regulatory Activities
mNIS	Modified Neuropathy Impairment Score
mRNA	Messenger ribonucleic acid
NCS	Nerve conduction studies
NIS	Neuropathy Impairment Score
NT-proBNP	N-terminal prohormone of B-type natriuretic peptide
PD	Pharmacodynamic
PK	Pharmacokinetic
PND	Polyneuropathy disability
PO	By mouth
QST	Quantitative sensory testing
QTc	QT interval corrected for heart rate
RBP	Retinol binding protein

Abbreviation	Definition
Rel Day	Relative study day
RNAi	Ribonucleic interference
R-ODS	Rasch-built Overall Disability Scale
SAE	Serious adverse event
SAP	Statistical analysis plan
SD	Standard deviation
SGNFD	Sweat gland nerve fiber density
SI	International system of units
siRNA	Small interfering ribonucleic acid
SOC	System organ class
T4	Thyroxine
TP	Touch pressure
TTR	Transthyretin
VAS	Visual analogue scale
VDT	Vibration detection threshold
WHO	World Health Organization
WT	Wild type

1. INFORMATION FROM THE STUDY PROTOCOL

1.1. Introduction and Objectives

1.1.1. Introduction

Transthyretin (TTR), also known as prealbumin, is a tetramer protein produced predominantly by hepatocytes (>95% of TTR is liver-derived), with a small fraction produced in the choroid plexus and retina [1]. The primary physiological role of TTR is to serve as a carrier of retinol (also known as vitamin A); it also plays a minor role as a carrier for thyroxine (T4).

Mutations in the TTR gene can lead to destabilization of the tetrameric protein and disassociation of the TTR subunits into dimers and individual monomers. These misfolded TTR monomers (both mutant and wild type [WT]) can then self-assemble into amyloid fibrils [1]. The amyloid fibrils are deposited into the extracellular space of various tissues where they form amyloid plaques, with the peripheral nervous system, gastrointestinal tract, and heart being the major sites of deposition.

There are over 100 reported TTR genetic mutations. These mutations are phenotypically expressed as a spectrum of disease which is collectively referred to as TTR-mediated amyloidosis (ATTR) [2]. There is a range of clinical manifestations of ATTR; the most common manifestations include some form of cardiac and/or neurologic involvement (e.g., cardiomyopathy, autonomic neuropathy, and sensory and motor neuropathy) that depends, in part, upon the particular TTR mutation and the site of amyloid deposition. Transthyretin amyloidosis is associated with severe morbidity and mortality, with a life expectancy limited to approximately 5 to 15 years from symptom onset [2].

Two significant clinical syndromes of ATTR have been described: familial amyloidotic polyneuropathy (FAP) and familial amyloidotic cardiomyopathy (FAC), both of which are characterized by amyloid deposits of both mutant and WT TTR [1].

Familial amyloidotic polyneuropathy, caused predominantly by the V30M mutation, occurs primarily in families with heritage from Portugal, Sweden and Japan, has an earlier onset (age 30 to 50 years), and is characterized initially by peripheral neuropathy leading to sensory and motor deficits, as well as profound autonomic dysfunction that produces disabling gastrointestinal pathology, orthostatic hypotension, and bladder dysfunction [1, 2]. Amyloid infiltration of the sinus node and atrioventricular conduction system in the heart is also common in FAP. Sudden death is not uncommon in FAP, and is believed to result from heart block or tachyarrhythmias [8, 9].

It is estimated that 45,000 to 50,000 individuals have FAP or FAC. In both FAP and FAC, quality of life is severely impacted following the onset of symptoms, and the disease proceeds inexorably to death [10, 11].

Because the liver is the primary source of mutant TTR, liver transplantation has been used over the past 20 years in an attempt to treat ATTR [1]. However, the procedure is only effective in halting or slowing the progression of disease in patients with an early age of onset [1], especially for those with the V30M mutation and short disease duration prior to transplant; consequently almost two-thirds of ATTR patients are not transplant-eligible. When performed early in the course of the disease, liver transplantation can stabilize and slow progression of neuropathy in patients with FAP due to V30M. However, in FAC patients and FAP patients with evidence of cardiac involvement, liver transplantation is contraindicated since it does not

halt the progression of cardiac disease in these patients [13, 14, 15, 16] and may actually accelerate the course of cardiomyopathy due to further deposition of WT TTR (originating from the transplanted liver) in the heart [1].

Tafamidis, a TTR tetramer stabilizer, was approved in November 2011 in the European Union (EU) for the treatment of ATTR in adult patients with stage 1 symptomatic polyneuropathy to delay peripheral neurologic impairment [1]; it has not been approved in the US. Diflunisal, is another TTR tetramer stabilizer available in generic form. A US government sponsored multicenter, placebo-controlled Phase 3 study in FAP patients was completed in 2012; data suggest an effect of diflunisal on NIS+7, the primary endpoint of the study [1].

However, the large majority of ATTR patients do not qualify for either liver transplantation or tafamidis, and therefore, the disease is primarily managed with palliative care.

Ribonucleic acid interference (RNAi) is a naturally occurring cellular mechanism for regulating gene expression that is mediated by “small interfering ribonucleic acids” (siRNAs) [1]. Typically, synthetic siRNAs are 19 to 23 base pair double-stranded oligonucleotides in a staggered duplex with a 2-nucleotide overhang at one or both of the 3' ends. Such siRNAs can be designed to target an endogenous or virally-expressed gene. When introduced into cells, the net effect of an RNAi-based pharmacological approach is the binding of the siRNA to its complementary messenger ribonucleic acid (mRNA) sequence, cleavage of this target mRNA, and suppression of the target protein [1]. The ability to selectively and potently degrade the mRNA encoding the TTR protein using an siRNA offers a potent and specific approach for the treatment of ATTR.

Patisiran Solution for Injection (hereafter referred to as patisiran), is a novel drug to treat ATTR and consists of a single LNP-formulated TTR siRNA targeting both WT and all known mutant forms of TTR. Since TTR amyloid deposits consist of both mutant and WT TTR, it is desirable to be able to lower the production of both WT and mutant TTR with a single drug in order to treat the different variants of ATTR. Patisiran is intended for administration as an intravenous (IV) infusion over 70 minutes.

